#### List of Abbreviations

AE: Adverse Event

ANOVA: Analysis of Variance BFI: Brief Fatigue Inventory BPI: Brief Pain Inventory CNS: Central Nervous System

CR: Complete Response CRF: Case Report Form

CT: Computerized Axial Tomography

CTCAE: Common Terminology Criteria (CTC) for Adverse Events

CTV: Clinical Target Volume

DSMB: Data and Safety Monitoring Board DSMC: Data and Safety Monitoring Committee

EBRT: External Beam Radiotherapy

ECG: Electrocardiogram

EORTC: European Organization for Research and Treatment of Cancer

EQ-5D: European Quality of Life Index

FACT-BR: Functional Assessment of Cancer Therapy-Brain FACT-G: Functional Assessment of Cancer Therapy-General

FDA: Food and Drug Administration

FDG: Fludeoxyglucose GTV: Gross Tumor Volume

Gy: Gray

HIPAA: Health Insurance Portability and Accountability Act

IUD: Intra-Uterine Device LET: Linear Energy Transfer

MRI: Magnetic Resonance Imaging NCI: National Cancer Institute OAR: Organ at Risk Volume

OER: Oxygen Enhancement Ratio PAR: Planning Organ at Risk Volume

PD: Progressive Disease

PBSTV: Pencil Beam Scanning Target Volume

PET: Positron Emission Tomography

PFS: Progression Free Survival PHI: Protected Health Information

PI: Principal Investigator PR: Partial Response

RC-REVIEW: Range Compensator Review Volume

RBE: Relative Biologic Effectiveness

RTOG: Radiation Therapy Oncology Group

SAE: Serious Adverse Event

SD: Stable Disease

SOBP: Spread Out Bragg Peak SOP: Standard Operating Procedure SWOG: Southwest Oncology Group WBC: White Blood Cell Count

# **Study Summary**

Title	Proton Beam Radiation for Chordomas and Chondrosarcomas
Short Title	
Protocol Number	UPCC#: 01310 IRB#: 811185
Phase	Feasibility and Phase II
Methodology	Open
Study Duration	Four years (enrollment)
Study Center(s)	University of Pennsylvania
Objectives	1) To evaluate the feasibility and acute side effects of proton therapy for chordomas and chondrosarcomas 2) To evaluate clinical outcomes and long term side effects of proton beam radiation for treatment of chordomas and chondrosarcomas
Number of Subjects	50 total = (12[feasibility] + 38 [Phase II])
Diagnosis and Main Inclusion Criteria	Chordoma or Chondrosarcoma, Age18 or greater, No prior radiation

#### 1 Introduction

# 1.1 Background

Chordomas are malignant tumors arising from embryonic notochord remnant. The majority of these tumors occur along the craniospinal axis: 50% grow in the sacrococcygeal regions, 35% in the base of the skull and 15% in the spine [1]; [2]. The incidence of chordoma is quite low. There is a slight male predominance in chordomas originating from the spinal cord, whereas lesions of the skull are seen more frequently in females. They have two age peaks of incidence, one in the fourth decade for skull lesions and one between the fifth and seventh decades for lesions that originate from the spinal cord and sacral region. Chondrosarcomas most commonly involve the femur with a striking predilection for the secondary ossification centers. Chondrosarcomas arising de novo present most commonly in the femur; and secondary chondrosarcomas are most prevalent in the ilium. They account for 10-20% of malignancy primary bone tumors. Age range is from 7 to 73 years with the most commons diagnosis between 30 and 60 years of age. Males predominate slightly in most series but mesenchymal chondrosarcoma occur more frequently in women. Conditions that predispose to chondrosarcoma include Ollier's disease, Paget's disease, Maffucci's syndrome, previous exposure to intravenous Thorotrast, chondromyxsoid fibroma and prior radiation therapy.

Chordomas have a slow growth and a tendency to destroy the bone locally. In their growth, they compress on adjacent tissues and structures, and this compression is responsible for most clinical symptoms. Although chordomas are essentially locally malignant tumors, they sometimes metastasize; the incidence of metastasis ranges from 10-25% [3]. They occur in the late phase of the disease or with a very large, massive primary lesion. Chondrosarcomas are locally aggressive lesion with a high propensity for local recurrence, which usually occurs within 5 years after treatment. Head and truncal chondrosarcomas have an 85% chance of recurring at the primary site. They usually follow a more indolent course. The most common site of distal metastases is the lungs, followed by bone, liver, kidney, breast and brain. Up to 10% of chondrosarcomas can dedifferentiate into aggressive fibrosarcomas or osteosarcomas.

The five year survival rate for patients with chordomas is around 80% while for chondrosarcomas is 100% [4, 5]. The standard treatment of choice remains to be treated with aggressive surgery. The standard surgical procedure is a wide total excision. The biopsy tract must be excised, and the tumor should not be exposed during the operative procedure. The recurrent rate can vary from 15% with "adequate" surgery to 87% with inadequate procedures. Close follow up is needed, as these tumors can relapse 10 years or more from surgery. Most problems in treating patients with chordomas derive from the location of the tumor. The proximity of the tumor mass remains the preferred method of treatment for spinal and sacrococcygeal chordomas. Survival after radical surgery is normally long, although most patients experience a local failure in the course of the disease. The role of radiation is these tumors are not completely defined. However, data supports the efficacy of irradiation as adjuvant treatment after incomplete surgical resection. When surgery is not possible, radiation therapy can be used as a single-modality treatment. Different techniques and different types of ionizing radiation have been used to overcome dose-limitation problems. Based on current data, a combination of surgery and postoperative irradiation can be considered standard

treatment for resectable chordomas. If surgery is not indicated because of the location of the tumor, radiation therapy as a single modality can be considered a standard procedure for definitive treatment.

Surgery is still considered the primary treatment for chordomas. However then surgical excision is incomplete or when surgery is not possible because of the tumor location, radiation can play a significant role. Particle beams and high linear energy transfer radiation represent an important alternative to the use of conventional photon beams in the treatment of lesions located in specific areas. Keisch and coworkers reported in 21 patients after incomplete resection, irradiation improved local tumor control and disease free survival especially in tumor originating in the lumbosacral regions [6]. Doses higher than 55 Gy showed a statistically significant improvement in duration of local tumor control when compared with lower doses in a report of Fuller and Bloom [7]. Chetiyawardana treated 48 patients with doses of 30-45 Gy with irradiation as adjuvant treatment after surgical resection. Stereotactic fractionated radiotherapy also has been used with promising results [8]. The study found a local relapse free survival of 82% at 2 years and 50% at 5 years with a corresponding overall survival rate of 40%. Since 1970s, particle beams have been used because they are considered more beneficial than conventional irradiation for their physical and biologic characteristics. There are two main considerations. The first is that they are located in areas in which a sharp collimation of the beam is essential to prevent the occurrence of severe side effects (e.g. base of skull). No prospective randomized trials compare the effectiveness of particle-beam versus conventional irradiation. However several retrospective studies have shown increased local tumor control when particle beams were used. The Proton Therapy Working group reviewed the matter in 2000 and reported a superior outcome for patients treated with heavy particles compared with those that received conventional therapy [9]. A radiotherapy schedule of mixed protons and photons for chordomas of the base of skull resulted in 60% local control at 5 years [4]. Suit et al treated chondrosarcomas of the cervical spine and base of skull with combined photonproton radiation therapy [10]. Total doses ranged from 65.3 to 75 GyE with photon doses between 21.3 and 39.6 Gy and protons doses from 28.7 to 40 GyE. The proton field was used as a cone down boost field. No central nervous system toxic effects were reported; survival times without evidence of disease ranged from 4 to 74 months.

The importance of particle beams, used alone or in combination with photons, in treating lesions originating from areas that are difficult to treat safely with conventional irradiation has been largely proved with a 5 year PFS of 70% [11]. Saunders et al treated 19 patients with lesions adjacent to critical CNS structures with a high local control rate 79% and only 2 cases of major side effects [12, 13]. Data confirmed in another study of 45 patients from the same institution showed a local control 59% and nine of 45 had significant side effects. Castro treated 31 patients with lesions originating near the brainstem or spinal cord. Local control was achieved in 62% and complications occurred in 13% [14].

Saunders reported on 87.5% local control in 8 cases of chordoma of the sacrum [12, 13]. Schoenthlaer and colleagues reports on 14 cases of sacrum chordoma with local control of 55% [15]. One two major complications were seen in these patients. Technical aspects such as precise positioning of the patient and immobilization are of paramount importance when

Version: 04/04/2014

particle beams. Further improvement especially in prevention of side effects is expected as 3D treatment planning programs become more available for daily clinical use.

Magnitude of effects is related directly to dose and field volume and is inversely related to age at the time of therapy. Endocrine dysfunction, visual changes, brainstem injury, or temporal lobe injury have been documented in around 5-10% [16]. Growth delays may results in limb joint dislocation secondary to underdeveloped joint fossa, mandibular or craniofacial abnormalities and dentition delay. Scoliosis after vertebral irradiation is possible but is usually not progressive and frequently is compensated by pelvic tilt. Inclusion of the entire width of the vertebral body in the treatment field does not appear to decrease the incidence of scoliosis. Because of radiation induced vascular changes, irradiated bone is more sensitive to infection, fracture and necrosis [17].

#### **Rationale for Proton Therapy:**

The goal of radiation therapy is to deposit most of the dose to the target while minimizing the dose to the surrounding normal tissues. Conventional photon radiotherapy deposits its dose along the entire beam path to the tumor or target volume as well as beyond the depth of the target. Techniques to minimize the dose to surrounding tissues such as using multiple beam angles, modulating the intensity of the radiation delivered through each beam have been utilized, however, these techniques still entail both entrance dose to normal tissue as it penetrates to reach a tumor at depth in tissue, and an exit dose as it exits the body in a straight path beyond the tumor. Proton radiotherapy differs from photon radiotherapy in that most of the energy is deposited at a specific depth known as the Bragg peak. The dose immediately beyond the Bragg peak is essentially zero, which allows tissues on the posterior side of the tumor to be spared. The clinical application of protons provides an improvement over photons in its ability to deliver a high-dose-volume to any configuration within an anatomical site while maintaining lower doses to surrounding normal tissues, resulting in decreased short and longterm morbidity, due to the unique Bragg Peak phenomenon of the dose distribution of protons. Theoretically, this should ease the current limitation of normal tissue tolerance as a doselimiting factor particularly for larger tumors as well as allow greater dose to be delivered to the tumor/target volume. The current protocol proposes to allow the use of protons (which is approved by the U.S. Food and Drug Administration) for the treatment of chordomas and chondrosarcomas of the base of skull.

Protons have a similar biologic effect to photons against tumors. The biological effect of radiation is dependent on its linear energy transfer (LET). LET is defined as the rate of energy transferred by ionizing radiation per unit path length. To compare different types of radiation, we use the relative biologic effectiveness (RBE), which is defined as the ratio of the dose of particle radiation to the dose of 60Co radiation producing the same biological endpoint. Standard photon radiation therapy has a RBE of 1.0; the RBE of protons is thought to be between 1.05 to 1.25[18-20]. A recent review of in vivo and in vitro experiments concluded that RBE varies with dose or dose per fraction and increases with an increasing depth in the spread out Bragg Peak (SOBP) and is most significant at the distal edge of the SOBP. Overall though, based on the data to date, an average RBE of approximately 1.1 in the entrance of the SOBP is reasonable to assume[21]. The clinical advantage of proton beam radiotherapy over standard photon radiation results from the more favorable dose distributions achievable with its

particular physical properties as previously described. The advantage of protons has been demonstrated for medulloblastoma and, prostate cancer, and comparative treatment planning using protons versus photons have shown a clear advantage to protons in terms of dose distribution [22-27].

# 2 Study Objectives

This study will be done in two phases. In the first phase, feasibility will be established using the primary objectives set below. The second phase will begin no earlier than 90 days after the last patient in the initial phase has started treatment and once safety and feasibility has been verified. The secondary objectives will serve as the objectives for the second phase of the study.

#### **Primary Objective**

The primary objective of this study is feasibility. The study will be deemed infeasible if greater than 10% of pts experience one of the following:

- a. Patient cannot be given treatment because anatomy is such that a dosimetrically satisfactory treatment plan cannot be devised as defined in Section 4.5.1.
- b. For base of skull patients only. Patient receives greater than 40% of their total treatment (for any reason, i.e. unable to set patient up within acceptable limits of tolerance, patient unable to tolerate treatment position or immobilization for duration of treatment) with photon beam radiotherapy (using a backup photon plan).

For spine and all other patients. Patient receives greater than 20% of their total treatment (for any reason, i.e. unable to set patient up within acceptable limits of tolerance, patient unable to tolerate treatment position or immobilization for duration of treatment) with photon beam radiotherapy (using a backup photon plan).

- c. Patient is unable to complete all of his/her treatments within 10 days of estimated date of treatment completion or requires a treatment break greater than 5 days.
- d. Additionally, no greater than 20% of patients experience an unexpected acute toxicity > Grade 3 that is probably or definitely related to radiation therapy.

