#### **4.6** Treatment Duration

Proton radiation therapy will in most instances be completed within 9 weeks of the start of treatment. This may be extended if subjects require a break from treatment. Criteria for break would include any **Grade 3 or 4** toxicity, depending on the clinical situation as determined by the treating physician. All subjects experiencing Grade 4 toxicity considered probably or definitely related to radiation will be considered infeasible in the feasibility phase of the study.

Version: 04/04/2014

Continuation of treatment and/or further treatment plans will be decided at the discretion of their treating physician.

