### 7.1.2 Endpoints

### 7.1.2.1 Primary Endpoints

Feasibility will be based on multiple radiation planning and treatment parameters. For proton to be deemed feasible, no greater than 10% of patients should experience one of the following events: a) Patient cannot be given treatment because anatomy is such that a dosimetrically satisfactory treatment plan cannot be devised. For example, the dosimetry is unsatisfactory if

<95% of target volume is covered by 95% of the dose, b) Patient receives greater than 50% of their total treatment (for any reason-unable to set patient up within acceptable limits of tolerance, patient unable to tolerate treatment position or immobilization for duration of treatment) with photon beam radiotherapy (using a backup photon plan, c) Patient is unable to complete all of his/her treatments within 10 days of estimated date of treatment completion or requires a treatment break greater than 5 days.

Acute Toxicity is defined as any grade 3 or higher toxicity, considered probably or definitely related to radiation, observed within 90 days from start of therapy, excluding cranial nerve palsies or nerve root symptoms as these may be due to the tumor itself or prior surgery. Toxicities will be graded using the NCI Common Terminology Criteria for Adverse Events (CTCAE) Version 4.0.

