#### **Feasibility**

A feasibility rate  $\geq 90\%$  is considered acceptable. We will assume a beta (5,1) prior, which is information equivalent to feasibility established in 5 of 6 treated patients. If the number of patients in whom proton is deemed feasible is less than or equal to the number in the table below then termination will be considered as it is highly unlikely that the feasibility rate is  $\geq 90\%$ , as noted by the Bayesian posterior probabilities.

D ' D 1	C D '1 '1'	• ,				
Bayesian Rule	for Feasibili	ıty				
Patients treated in each stratum	3	6	9	1		
				2		
Patients in whom proton is	1	4	6	9		
feasible						
Posterior Prob[feasibility rate	0	0	0	0		
>90%]		•	•	•		
	0	0	0	0		
	4	9	4	8		
Action	Т	Terminate enrollment				

Acute toxicity will be divided into 2 categories to best characterize toxicities in this disease. Non-Neurologic Acute Toxicity

Because proton therapy is expected to spare normal tissues, a non-neurologic acute toxicity rate  $\leq 20\%$  is considered acceptable. We will assume a beta (1,5) prior, which is information equivalent to toxicity in of treated patients. If the number of patients with non-neurologic acute toxicity equals or exceeds the number in the table, then termination will be considered as it is likely that the toxicity rate is >10%, as noted by the Bayesian posterior probabilities.

Bayesian Rule for Non-Neurologic Acute Toxicity						
Patients treated	3	6	9	1		
				2		
Patients who experience acute	2	2	3	4		
toxicity						
Posterior Prob[toxicity rate	0	0	0	0		
>20%]			•			
	8	6	7	7		
	0	2	0	6		
Action	Te	Terminate enrollment				

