#### Neurologic Acute Toxicity

Because radiation therapy is directed to the craniospinal axis, a neurologic acute toxicity rate  $\leq 10\%$  is considered acceptable. We will assume a beta (1,5) prior, which is information equivalent to acute neurologic toxicity in one of 6 treated patients. If the number of patients with neurologic acute toxicity equals or exceeds the number in the table, then termination will be considered as it is likely that the toxicity rate is  $\geq 10\%$ , as noted by the Bayesian posterior probabilities.

Bayesian Rule for Neurologic Acute Toxicity					
Patients treated 3 6 9 1					
				2	

Patients who experience acute toxicity	1	1	2	2	
Posterior Prob[toxicity rate	0	0	0	0	
>10%]		7	Q	. 7	
	1	0	4	6	
Action	To	erminate e	nrollment		

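### The acute-toxicity criterion that gates Phase II is stated differently in Sections 2(d), 4.6, 7.1.2.1 and 7.1.3, and no section says which version decides

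*Combined protocol and SAP*

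**What the plan says.** Four places in the current text bear on acute safety in the first phase.

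- **Section 2, Primary Objective.** The lead-in reads "The study will be deemed infeasible if greater than 10% of pts experience one of the following". Item (d) in the same list has its own limit: "no greater than 20% of patients experience an unexpected acute toxicity > Grade 3 that is probably or definitely related to radiation therapy". It gives no time window, no exclusions and no split by toxicity type.
- **Section 7.1.2.1, Primary Endpoints.** The safety endpoint "is defined as any grade 3 or higher toxicity, considered probably or definitely related to radiation, observed within 90 days from start of therapy". Some neurologic findings are then left out of the count, the wording being "excluding cranial nerve palsies or nerve root symptoms as these may be due to the tumor itself or prior surgery". Expectedness plays no part. Feasibility is a separate endpoint, for which "no greater than 10% of patients should experience one of the following events", and its items (a) to (c) include no toxicity.
- **Section 7.1.3, Rules for Early Termination.** Acute toxicity "will be divided into 2 categories to best characterize toxicities in this disease". A non-neurologic rate up to 20% and a neurologic rate up to 10% are acceptable. Each category has a Bayesian count table with a Beta(1,5) prior, described in the neurologic rule as one "which is information equivalent to acute neurologic toxicity in one of 6 treated patients". At 12 patients the boundaries are 4 non-neurologic or 2 neurologic events. The non-neurologic sentence names a 10% threshold, while its table is headed 20%.
- **Section 4.6, Treatment Duration.** Every subject with a related Grade 4 toxicity "will be considered infeasible in the feasibility phase of the study". No proportion is attached. Neither Section 2(a)-(c) nor Section 7.1.2.1(a)-(c) lists this event.

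The opening of Section 2 makes Phase II conditional on verified safety and feasibility. Section 7.2 makes it conditional on both being established in the first 12 patients. Neither says which toxicity definition is meant.

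**The concern.** Acute toxicity is one of the two primary objectives of the first phase (Section 7.1.1), and further enrollment depends on it. The versions differ in grade, expectedness, exclusions, pooling and limit. The same 12 patients can therefore satisfy one version and fail another. If the choice is made after the toxicity data are known, the gate decision can follow the choice of section instead of the data, and a reader of the results could not tell which criterion had been fixed in advance.

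**Working it through.** **Inputs.** Beta(1,5) prior, boundaries and printed posteriors from Section 7.1.3; limits of 20% and 10% from Sections 2 and 7.1.2.1; n = 12 from Sections 7.1.1 and 7.2.

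**Formula.** With x events in n patients, P(rate > c) = 1 − F(c; 1 + x, 5 + n − x), where F is the beta distribution function. For feasibility, with x feasible patients and a Beta(5,1) prior, P(rate > 0.90) = 1 − F(0.90; 5 + x, 1 + n − x).

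**The plan's own tables reproduce.**

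| Rule | Boundary | Printed | Recomputed |
|---|---|---|---|
| Non-neurologic, c = 0.20 | 2/3, 2/6, 3/9, 4/12 | 0.80, 0.62, 0.70, 0.76 | 0.797, 0.617, 0.698, 0.758 |
| Neurologic, c = 0.10 | 1/3, 1/6, 2/9, 2/12 | 0.81, 0.70, 0.84, 0.76 | 0.813, 0.697, 0.842, 0.762 |
| Feasibility, rate > 0.90 | 1/3, 4/6, 6/9, 9/12 | 0.04, 0.09, 0.04, 0.08 | 0.038, 0.090, 0.044, 0.083 |

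The boundaries are therefore sound as calculated. With c = 0.10 the non-neurologic value at 4/12 would be 0.978, not 0.76. The 10% in that sentence is thus the slip and the 20% in the table is what was calculated. Section 7.2.3 repeats the sentence with 20%.

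**Smallest count that fails each rule at n = 12.**

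- Section 2(d): 3 patients (3/12 = 25%; 2/12 = 16.7% passes).
- Section 7.1.3: 4 non-neurologic or 2 neurologic.
- 10% feasibility limit: 2 patients (2/12 = 16.7%; 1/12 = 8.3% passes).

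**The same data under each rule, at the 12-patient look.**

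| Related events in 12 patients | Section 2(d) | Section 7.1.3 toxicity table |
|---|---|---|
| 4 expected Grade 3, non-neurologic | 0/12, passes | 4/12, reached (0.758) |
| 2 Grade 3, neurologic, not cranial nerve or nerve root | at most 2/12 = 16.7%, passes | 2/12, reached (0.762) |
| 3 unexpected Grade 4, non-neurologic | 3/12 = 25%, fails | boundary 4, not reached (0.549) |
| 2 Grade 4, non-neurologic | at most 16.7%, passes | boundary 4, not reached (0.310) |

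In the last two rows the earlier looks must also have been passed: no more than one of the events in the first 6 patients and, in the third row, no more than two in the first 9.

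**Section 4.6.** Suppose its Grade 4 patients fall under the 10% feasibility limit. This is an inference, because 4.6 gives no limit.

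- In the last row, 2/12 = 16.7% exceeds 10%, yet 10 of 12 feasible lies above the Bayesian feasibility boundary of 9.
- In the third row, 9 of 12 feasible meets that boundary. Whether the third row triggers any Section 7.1.3 rule at 12 patients therefore depends on where Grade 4 events are counted.

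**Same event, different limits.** If both sections counted the same non-neurologic event and its true rate were 20%, the binomial chance of at least 3 of 12 is 0.442 and of at least 4 of 12 is 0.205. The two rules would then disagree with probability of about 0.442 − 0.205 = 0.24 at that single look.

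**The case against.** The strongest reply is that the sections do different jobs. Section 2(d) is an end-of-phase criterion. Section 7.1.3 is an early-termination rule under which stopping is to be considered, and Section 8.4 refers all stopping rules to Section 7. That reply stands against a stronger reading that a reader might infer: that the study could declare safety under 2(d) at a toxicity level where the tables call for termination. The first two patterns in the working trigger the Section 7.1.3 rule whatever 2(d) says, and no section lets 2(d) override it. The reply does not settle the gate. Section 7.1.3 holds the only numeric toxicity limits in Section 7 before Phase II, its tables run to exactly 12 patients, and neither gate statement says how the two sections combine.

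Feasibility and toxicity are also separate endpoints, so failing one and passing the other is not in itself a contradiction. This stands, and together with the missing limit in Section 4.6 it makes the Grade 4 conflict conditional. The event's absence from both feasibility lists is a gap regardless.

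The sign before Grade 3 in 2(d) may be a greater-or-equal sign lost in the PDF text. That would remove the grade difference only. Expectedness, pooling, exclusions and limits would still differ, and the four patterns would give the same results.

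The 20% limit does appear in both 2(d) and the non-neurologic rule. The limits still differ through pooling, the separate 10% neurologic limit, and the failing counts of 3 against 4.

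**Conclusion.** The acute-safety criterion for opening Phase II is ambiguous, and the ambiguity can change the decision. At 12 patients Section 2(d) is more lenient than Section 7.1.3 for expected Grade 3 events and for two neurologic events. It is stricter for three unexpected Grade 4 non-neurologic events. Nor would moving 2(d) to the Section 7.1.2.1 definition simply tighten it, as a reader might assume: that third pattern would then pass the toxicity rule, and the cranial nerve and nerve root exclusion would enter the primary objective.

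The documents do not show that the termination tables can be bypassed.

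The conclusion rests on three assumptions. The gate is taken at 12 patients, as Section 7.2 states. Section 7.1.4 analyzes feasibility on 17 and 26 patients, where exceeding 20% means 4 and 6 patients and Section 7.1.3 has no row. The events in each pattern are taken as probably or definitely related and within the acute window. Any failure through Section 4.6 rests on the inferred 10% limit.

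**What to change.** Reconcile Sections 2(d), 4.6, 7.1.2.1 and 7.1.3 as follows.

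1. State one acute-toxicity event: grade, whether expectedness matters, exclusions and time window. Section 8.1 ends the acute period at post-treatment day 90, while Section 7.1.2.1 counts from the start of therapy, so the window needs settling too.
2. State one set of limits, and say whether neurologic and non-neurologic events are judged separately or pooled. If separately, define the two categories.
3. State one decision rule for the gate to Phase II, including how it relates to the early-termination tables and the number of patients it uses.
4. Say once whether a related Grade 4 event counts under feasibility or under toxicity. If under feasibility, add it to both lists with its limit.
5. Correct the 10% in the non-neurologic sentence of Section 7.1.3 to match its 20% table.

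The choice of clinical definition is the sponsor's. If it differs from Section 7.1.2.1, confirm that the acceptable rates and boundaries in Section 7.1.3 still suit it.

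The cost is a wording amendment. No new data are needed, because toxicities are already graded and attributed. The downside is that the Section 2 criterion may become stricter for some event patterns and looser for others, and the amendment should say so.
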